## Section 2: Introduction

Section/Item	Index	Description
Background and Introduction	7	
Clopidogrel is a thienopyridine antiplatelet agent, which inhibits the purinergic P2Y12 receptor on platelets and prevents their aggregation. It is commonly used in patients with acute coronary syndromes (ACS) undergoing percutaneous coronary intervention (PCI). CYP2C19 is one of the principal enzymes involved in the bioactivation of clopidogrel from the pro-drug to its active metabolite. The most common loss of function (LOF) allele is *2 (c.681G>A; rs4244285), with frequencies of ~15% in Caucasians and Africans and 29-35% in Asians. A large meta-analysis performed by Mega and colleagues demonstrated that CYP2C19*2 carriers treated with clopidogrel have a higher risk for major adverse cardiac events compared to noncarriers (hazard ratio (HR) of 1.55, 95%CI 1.11-2.17 for heterozygotes; HR 1.76, 95% CI 1.24-2.50) and higher risk of stent thrombosis (HR 2.67, 95% CI 1.69-4.22 for heterozygotes; HR 3.97, 95% CI 1.75-9.02 for homozygotes). Therefore, clopidogrel is less effective in patients who are CYP2C19 poor metabolizers and alternative therapy is recommended.
 
While a body of observational literature and clinical guidelines suggest prescribing alternative antiplatelet therapy in carriers of CYP2C19 LOF alleles, it is unknown whether physicians will follow genotype guided recommendations when pharmacogenetic (PGx) results are presented to them in a real world setting. To provide evidence regarding the implementation and effectiveness of PGx testing following PCI, we examined the differences in prescribing of antiplatelet drugs when presented with genotype data. We also evaluated physician's adherence to the genotype guided antiplatelet recommendations.

Objectives	8	
 
1. To determine the effect of CYP2C19 genotyping on the prescribing patterns of antiplatelet therapies following cardiac catheterization.
 
2. To determine the rates of clinical outcomes.
 
3. To identify factors linked with successful implementation of clinical pharmacogenetic (PGx) testing in a large academic medical center.
 

### Section 3: Study Methods

Section/Item	Index	Description
Trial Design	9	This was a prospective, pragmatic, randomized, controlled clinical pharmacogenetic implementation trial. Patients undergoing PCI with stent implantation requiring anti-platelet therapy were randomized 1:1 to either rapid genotyping of CYP2C19 with reporting of results to the interventional cardiologist or no genotyping (usual care).
Randomization	10	We used Stata's V13.1 (College Lake, TX) random number generator to draw random numbers that were used to randomize participants to the genotyping and usual care groups. Randomization was stratified by hospital site and by the presence or absence of ACS. Acute coronary syndrome was defined as unstable angina, non-ST elevation myocardial infarction, or ST-elevation myocardial infarction. The designation of ACS vs. stable angina was made by the treating interventional cardiologist. Within each of the four groups, randomization was balanced so that after every 10 patients, 5 were randomized to the genotyped group and 5 to usual care.
Sample size	11	The sample size calculation was based on two factors: 1) the rate of pre-study prasugrel/ticagrelor use (20%) and 2) anticipated increase in prasugrel/ticagrelor prescribing based on the frequency CYP2C19 LOF variants (~30-35%). We estimated a 15% difference in the use of prasugrel/ticagrelor in the two groups (35% in the genotyped group and 20% in the control group). A sample size of 138 per group (a total of 276) would provide 80% power at an alpha level of 0.05 to detect this difference. We increased our sample size to ~250 per group to allow for subgroup comparisons (e.g. ACS vs. stable coronary disease).
Framework	12	Genotyping will increase the prescribing of prasugrel or ticagrelor from the baseline rate of 20%.
Statistical interim analyses and stopping guidance	13	No interim analyses planned.
Timing of final analysis	14	Participants were followed until May 31, 2017 for prospective clinical endpoints assessment with the intention of a 12 month follow-up time for each participant. All analyses were performed collectively after May 31, 2017.
Timing of outcome assessment	15	Participants were called by telephone every 3 months ± 2 weeks following randomization to assess occurrence of clinical endpoints. Medical records were requested for admissions that occurred outside UPHS. Medical records within UPHS were reviewed simultaneously to assess additional clinical outcomes not reported by participants.

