### 7.1 Primary endpoints

1. We will tabulate the number and proportion of prasugrel/ticagrelor in each Arm. We will compare discharge antiplatelet therapy choice between the genotype and control arm using the chi-square or Fisher's exact test. The probability of receipt of antiplatelet agents will be determined by logistic regression.

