### 7.2 Secondary endpoints

1. Implementation.
  - a. We will estimate adherence to suggested treatment recommendations based on results of the *CYP2C19* genetic test. The adherence rate is defined as the number of participants in Arm 1 with LOF variants that received prasugrel or ticagrelor + the number of participants without these variants that received clopidogrel divided by the total number in Arm 1.
  - b. We will tabulate reasons for non-adherence to recommendations.
2. Clinical outcomes.
  - a. Frequencies of CV related death, MI, stroke urgent, need for revascularization and stent thrombosis will be reported as will frequencies of bleeding complications. We will determine time to first major cardiac event as a composite endpoint (CV related death, MI, stroke urgent need for revascularization and stent thrombosis). The incidence of first MACE and first major bleeding events between the groups will be compared by use of Kaplan-Meier estimators and statistical tests will be evaluated based on log-rank tests.
  - b. To determine whether MACE outcomes differ in participants with ACS, an interaction term between ACS and group assignment will be tested in a Cox proportional hazard model.
3. Medical service utilization. We will develop descriptive statistics for use of antiplatelet drugs, use of other cardiovascular medications, number of hospitalizations, number of physician visits, and use of rehabilitation services
4. Direct medical cost. We will also develop descriptive statistics for total cost, *CYP2C19* genetic testing cost, medication cost, hospitalization cost, physician visit cost, and rehabilitation cost.
5. Preference scores / QALYs. We will develop descriptive statistics for the SF-12 physical and mental scale scores, the SF-6D, a preference-based health-related quality of life score that can be derived from the SF-12, and for QALYs, a composite measure of its quality (based on the SF-6D). We will also report the correlation between the difference in cost and difference in QALYs (this correlation will be used in sample size estimation for the full study that this pilot study is designed to support).
6. Incremental cost-effectiveness ratio. Based on the differences in primary outcomes total cost and QALYs, we will calculate the ratio incremental costs divided by incremental QALYs, the 95% CI for this ratio, and the cost-effectiveness acceptability curve.

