### **7.5 Sample size for Primary Outcome**

The sample size calculation is based on two factors: 1) the rate of pre-study prasugrel/ticagrelor antiplatelet therapy prescribing (20%) and 2) anticipated increase in alternative antiplatelet prescribing based on the frequency CYP2C19 LOF variants (~30-35%). We estimate a 15% difference in the use of prasugrel/ticagrelor prescriptions in the two groups (35% in the genotype group and 20% in the control group). A sample size of 138 per group (a total of 276) would provide 80% power at an alpha level of 0.05 to detect this difference. We will increase our sample size to ~250 per group to allow for subgroup comparisons (e.g. ACS vs. stable coronary disease).

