## Section 4: Statistical Principles

Section/Item	Index	Description
Confidence intervals and p-value	16	The primary outcome was claimed at an alpha level of $p=0.05$ .
	17	No corrections were made for multiple testing.
	18	Confidence intervals pertaining to the probability of receipt of antiplatelet agents were reported.
Adherence and protocol deviations	19a	Adherence to the genotype guided recommendations was assessed in the genotyped group by comparing the discharge antiplatelet medication to those recommended by the CPIC guidelines. The research coordinator asked the prescribing cardiologists to provide any reasons for non-adherence. Adherence was not described in the usual care group as prescribing decisions were made by the cardiologist as per usual care.
	19b	The adherence rate was defined as the number of participants in genotyped group with LOF variants that received prasugrel or ticagrelor + the number of participants without these variants that received clopidogrel divided by the total number in this group
	19c	The only protocol deviations that were encountered in this trial were enrollment of participants that did not meet the inclusion/exclusion criteria. Since this was a pragmatic clinical trial, most of the procedures were performed within the context of usual care.
	19d	Participants that did not meet inclusion/exclusion criteria and were withdrawn from the study by the treating physician or study staff.
Analysis population	20	Modified intent to treat (removing the participants that did not meet the inclusion criteria).

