Analysis methods	27a	
Primary outcome: Discharge antiplatelet therapy choice by genotyped and usual care group was compared using the chi-square or Fisher's exact test. The probability of receipt of antiplatelet agents was determined by logistic regression.
 
Secondary outcomes:
 
 
1. The adherence rate to the genotype guided recommendations for the genotyped group was determined by reporting the number of participants with LOF variants that received prasugrel or ticagrelor + the number of participants without these variants that received clopidogrel divided by the total number in the genotyped arm.
 
2. Clinical outcomes. Frequencies of CV related death, MI, stroke urgent, need for revascularization and stent thrombosis was reported as well frequencies of bleeding complications and compared using chi-square test or Fisher's exact test when appropriate. The time to first major cardiac event as a composite endpoint (CV related death, MI, stroke urgent need for revascularization and stent thrombosis) was determined. The incidence of first MACE and first major bleeding events between the groups was compared by use of Kaplan-Meier estimators and statistical tests evaluated based on log-rank tests.
 
3. Implementation. The turnaround time for test result in the
 

		genotyped group was presented as mean ± standard deviation (hours).
27b	n/a	
27c	n/a	
27d	n/a	
27e	n/a	
27f		To evaluate whether genotyping influenced MACE outcomes in participants with ACS, an interaction term between ACS and group assignment was tested in a Cox proportional hazard model.
Missing data	28	For time to MACE analysis, participants were censored at the date of event or time of known last follow-up.

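### Enrolment was raised for ACS-versus-stable comparisons and randomisation was stratified, but the specified prescribing analysis gives no ACS breakdown and its primary test ignores the strata: a low-cost improvement

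*SAP*

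**What the plan says.** **Sample size.** Protocol 7.5, headed as the sample size for the primary outcome, takes prescribing rates of 35% and 20% and states: "A sample size of 138 per group (a total of 276) would provide 80% power". It continues: "We will increase our sample size to ~250 per group to allow for subgroup comparisons (e.g. ACS vs. stable coronary disease". SAP Section 3, item 11 repeats the calculation and the reason for the increase: "We increased our sample size to ~250 per group to allow for subgroup comparisons (e.g. ACS vs. stable coronary disease". Neither names the outcome of the subgroup comparisons or gives power for them.

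**Randomisation.** SAP Section 3, item 10 stratifies by hospital site and by ACS, giving four strata, each balanced 5:5 in every 10 patients. Protocol 4.0 names ACS as the only stratification factor.

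**Primary analysis.** Protocol 7.1: "We will compare discharge antiplatelet therapy choice between the genotype and control arm using the chi-square or Fisher's exact test". SAP Section 6, item 27a: "Discharge antiplatelet therapy choice by genotyped and usual care group was compared using the chi-square or Fisher's exact test", followed by "The probability of receipt of antiplatelet agents was determined by logistic regression". No model terms are given. Items 27b to 27e are marked not applicable. SAP Section 4, item 18 adds: "Confidence intervals pertaining to the probability of receipt of antiplatelet agents were reported".

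**ACS-by-arm analysis.** Protocol 7.2, item 2b has the only one: "To determine whether MACE outcomes differ in participants with ACS, an interaction term between ACS and group assignment will be tested in a Cox" model. SAP item 27f matches it. Both concern MACE, a secondary outcome.

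**The concern.** Two features of the design are not carried into the analysis of prescribing. ACS status was important enough to stratify on, and ACS versus stable disease is the example given for enrolling about 112 more patients per group than the primary test needed. Yet the prescribing analysis has no stated place for ACS.

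Two things are at stake, both modest. First, a reader cannot tell from the plan whether the effect of genotyping on prescribing would be estimated separately in ACS and stable disease, or how. With the model terms unnamed, that choice could be made after seeing the data. Second, a test that ignores strata which predict the outcome overstates its own standard error, so it gives up a little power and reports intervals slightly too wide.

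**Working it through.** **1. The plan's own figure.** Inputs (protocol 7.5, SAP item 11): p0 = 0.20, p1 = 0.35, alpha 0.05, power 80%. Sidedness is not stated; two-sided reproduces the figure. With mean rate 0.275:

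n = [1.96 × √(2 × 0.275 × 0.725) + 0.842 × √(0.20 × 0.80 + 0.35 × 0.65)]² / 0.15²
= [1.238 + 0.524]² / 0.0225 ≈ 138 per group. This matches.

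**2. Power at the enlarged size.** Power = Φ[(0.15√n − 1.238) / 0.6225].

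- n = 138: 80.0%
- n = 250: Φ[(2.372 − 1.238) / 0.6225] = Φ(1.82) = 96.6%

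The extra 2 × (250 − 138) = 224 patients were not needed for the primary test.

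**3. Cost of ignoring the strata.** The ACS share and the control rates by ACS status are not in the documents. Assume half ACS, 125 per arm in each of two ACS strata, and control rates averaging 20%. Site is left out of this check. The unstratified test uses variance 0.20 × 0.80 = 0.16. The variance that applies under stratified allocation is the mean of p(1 − p) over the strata. The effective critical value is therefore 1.96 × √(0.16 / within-stratum variance):

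| Control rates, ACS/stable | Within-stratum variance | Effective critical value | True two-sided error |
|---|---|---|---|
| 25/15 | 0.1575 | 1.98 | 4.8% |
| 30/10 | 0.1500 | 2.02 | 4.3% |
| 35/5 | 0.1375 | 2.11 | 3.5% |
| 38/2 | 0.1276 | 2.19 | 2.8% |

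Simulation (400,000 trials per row) gives the same error rates, against 4.9% to 5.0% for a Cochran-Mantel-Haenszel (CMH) test. Simulated power at the planned 15 points, unstratified versus CMH, in the same row order: 96.8 vs 96.8, 97.0 vs 97.4, 97.5 vs 98.1 and 97.8 vs 98.7. The largest loss is 0.9 points.

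The loss grows if the true effect is smaller. At 10 points (200,000 trials), power is 74.3% vs 76.0% for 30/10 and 75.2% vs 79.2% for 35/5.

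**4. Precision of an ACS breakdown.** Assume 250 per arm and 35% versus 20% in each subgroup. The variance sum is 0.16 + 0.2275 = 0.3875.

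- Half ACS (125 per arm per subgroup): SE = √(0.3875 / 125) = 0.0557, so the 95% CI is ±10.9 points.
- ACS share 30% to 70%: subgroups of 75 and 175 per arm give ±14.1 and ±9.2 points.
- Difference between the two subgroup effects, half ACS: SE = √(2 × 0.3875 / 125) = 0.0787. For 80% power the difference must be 2.80 × 0.0787 ≈ 22 points (about 24 at a 30% or 70% share).
- Example keeping the planned 15-point average: effects of 22.5 and 7.5 points from 20% control rates. SE = √[(0.4044 + 0.3594) / 125] = 0.0782, and power = Φ(0.15 / 0.0782 − 1.96) ≈ 48%.

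**The case against.** **The promised comparison may be the MACE one.** The sample size text names no outcome, and an ACS-by-arm analysis of MACE is specified in both documents. This stands in part. A reader might infer that the plan promised a powered ACS subgroup test of prescribing and dropped it. The documents do not support that: they promise no subgroup power, and the link to prescribing is an inference from where the sentence sits and from the absence of any MACE event calculation. Equally, it would be wrong to say that no ACS analysis was planned.

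**The logistic model may have included ACS and site.** The objective of finding factors linked with successful implementation makes that plausible. Against it, the one SAP model with a stated covariate list (the post-hoc Cox model, item 29) names site and ACS explicitly. The text does not settle the question, so disregard of the strata is certain only for the chi-square/Fisher test.

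**The added patients serve other aims.** Correct. The synopsis gives 500 to 600 subjects, and the economic calculation in protocol 7.6 works with 350 per arm. Enrolment beyond 276 was not wasted.

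**The strata gain is trivial.** At the planned effect it is. A reader might also suppose that an unstratified test after stratified randomisation inflates false positives. It does the reverse.

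**Intervals are already planned.** Protocol 7.0 and SAP item 18 do provide for confidence intervals. Only the breakdown by ACS and the named model terms would be new.

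**Conclusion.** The point holds as an inexpensive improvement, not as a flaw that threatens the result. The overall comparison is valid and has 96.6% power at 250 per group under the plan's own rates. The unstratified test is conservative to the extent that ACS predicts prescribing: its true error is 4.8% to 2.8% across the assumed control rates, with under 1 point of power lost at the planned effect.

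The more useful gap is the missing ACS breakdown of prescribing, since ACS versus stable disease is the plan's own example of why enrolment was raised. Such a breakdown could give only moderate precision, about ±11 points per subgroup if half are ACS, and could reliably detect only a difference in effects of about 22 points. That supports estimation rather than a subgroup claim.

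All subgroup and strata figures rest on an assumed ACS share and assumed control rates by ACS status. The protocol and SAP also disagree on whether site was a stratification factor.

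**What to change.** 1. Analyse the primary outcome with a CMH test stratified by site × ACS, or fit the logistic model with arm, site and ACS as named terms and report a standardised risk difference with 95% CI.
2. In a separate model, add an arm-by-ACS term. Report the arm difference in prasugrel/ticagrelor use with 95% CI within ACS and within stable disease, as estimates only. State the scale of the interaction, because a logistic term tests odds ratios while the precision figures above are for risk differences.
3. State which outcome the ACS-versus-stable comparisons concern.
4. Reconcile protocol 4.0 with SAP item 10 on the stratification factors.

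Arm, site, ACS status and discharge drug are already recorded, so the cost is a short analysis and a few sentences. The SAP is written in the past tense and places all analyses after May 31, 2017. Anything added after the data were analysed should therefore be labelled supplementary and shown beside the planned chi-square/Fisher result, which stays as the primary result.

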## Section 4: Statistical Principles

Section/Item	Index	Description
Confidence intervals and p-value	16	The primary outcome was claimed at an alpha level of $p=0.05$ .
	17	No corrections were made for multiple testing.
	18	Confidence intervals pertaining to the probability of receipt of antiplatelet agents were reported.
Adherence and protocol deviations	19a	Adherence to the genotype guided recommendations was assessed in the genotyped group by comparing the discharge antiplatelet medication to those recommended by the CPIC guidelines. The research coordinator asked the prescribing cardiologists to provide any reasons for non-adherence. Adherence was not described in the usual care group as prescribing decisions were made by the cardiologist as per usual care.
	19b	The adherence rate was defined as the number of participants in genotyped group with LOF variants that received prasugrel or ticagrelor + the number of participants without these variants that received clopidogrel divided by the total number in this group
	19c	The only protocol deviations that were encountered in this trial were enrollment of participants that did not meet the inclusion/exclusion criteria. Since this was a pragmatic clinical trial, most of the procedures were performed within the context of usual care.
	19d	Participants that did not meet inclusion/exclusion criteria and were withdrawn from the study by the treating physician or study staff.
Analysis population	20	Modified intent to treat (removing the participants that did not meet the inclusion criteria).

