Secondary and Tertiary Objectives	
 
1. To determine physician adherence to genotype guided recommendations.
 
2. To determine clinical outcomes (myocardial infarction, stroke, stent thrombosis, revascularization, death and bleeding)
 
3. To determine means and variances needed for economic evaluation
 

	
including cost, QALYs, and the correlation between cost and effect.
 
 
To estimate the incremental cost per quality-adjusted life year (QALY) ratio
 
Assess patient and prescriber attitudes towards PGx testing.
 

Number of subjects	500-600
Inclusion criteria	
 
Male and female subjects, <math>\geq 18</math> to <math>\leq 80</math> years at time of study
 
Status post PCI with stent implantation requiring antiplatelet therapy
 
Willingness to comply with all study-related procedures
 

Exclusion criteria	
 
Pending imminent surgery placing patients at increased risk for bleeding with prasugrel or ticagrelor.
 
History of intracranial hemorrhage, transient ischemic attack (TIA), stroke
 
Active bleeding
 
Need for long-term anticoagulation (i.e. warfarin, dabigatran, rivaroxaban, apixaban, edoxaban, or lovenox).
 
Current or prior (within the past four weeks) treatment with voraxapar (Zontivity).
 
Severe renal or hepatic impairment
 
Treating physician does not want subject to participate
 

Statistical methodology	
For the primary outcome the number (proportion) of participants receiving prasugrel/ticagrelor in each randomized arm will be determined. The adherence rate will be determined as the number of participants in genotyped arm with LOF variants that received prasugrel or ticagrelor + the number of participants without these variants that received clopidogrel divided by the total number. For categorical variables, frequencies and percentages will be presented. For continuous variables, the number of subjects, mean, standard deviation, minimum, 25th percentile, median, 75th percentile and maximum will be presented. Reported differences will include standard errors and 95% CI. Analyses will be based on the modified intention to treat.

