### **4.0 STUDY DESIGN**

[figure not shown]
This is a randomized, prospective, pragmatic open label pilot study (Figure 1). Patients undergoing PCI with stent implantation, who require anti-platelet therapy, will be randomized to: Arm 1) genotype guided dosing of antiplatelet therapy or Arm 2) usual care. Randomization will be stratified by the occurrence of acute coronary syndrome (ACS).

In Arm 1, a buccal swab will be obtained from subjects immediately following PCI/stent, to determine *CYP2C19* genotype with the SpartanRx system. This arm provides pharmacogenetic information to help guide decision making: initiation of therapy with prasugrel or ticagrelor will be recommended for participants found to be slow metabolizers [1 or 2 loss-of-function (LOF) mutations (\*2 or \*3) in *CYP2C19*]; initiation of therapy with clopidogrel will be recommended for participants found to be normal metabolizers (*CYP2C19* \*1/\*1). See Table 1 and Appendix A. Antiplatelet choice will ultimately be decided by the treating physician taking into account all clinical factors.

In Arm 2, the choice of antiplatelet therapy will be decided by the treating physician as per usual care. DNA will be collected by –saliva sample and *CYP2C19* genotype will be determined at the completion of the study.

Subjects in both groups will complete baseline health related quality of life questionnaire (HrQoL). Subjects will be contacted every three months for clinical information, medical service utilization and HrQoL assessments. No specific recommendations will be made regarding use of vorapaxar, a recently approved anti-platelet agent for which guideline-based recommendations regarding genotyping are not available.

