### **6.2 Genotyping**

If randomized to Arm 1 (genotyping arm), the research coordinator will obtain a buccal swab for the PGx test on the Spartan Rx system. If randomized to Arm 2 (control group), a saliva sample will be obtained with the Oragene-DNA 500 kit (DNA Genotek, Ottawa, Canada) and the genotyping will be performed at the completion of the study. For Arm 2, DNA will be extracted from saliva using the QIAamp DNA mini kit (Qiagen, Valencia, CA). Samples will be genotyped using the Infinium Global Screening Array (Illumina, SanDiego, CA), a genome-wide genotyping array that also contains pharmacogenetic variants. Genotyping will be performed on Illumina's iScan System at the Center for Advanced Genomics at the Children's Hospital of Philadelphia. The *CYP2C19* SNPs of interest \*2 (rs4244285), \*3 (rs4986893) and \*17 (rs12248560) will be extracted from the array data.

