## 7.0 STATISTICAL ANALYSIS

Data collected in this study will be reported using summary tables and results will be displayed for each treatment arm. For categorical variables, frequencies and percentages will be presented. For continuous variables, the number of subjects, mean, standard deviation, minimum, 25th percentile, median, 75th percentile and maximum will be presented. Reported differences will include standard errors and 95% CI. Analyses will be based on the intention to treat. Continuous variables will be compared using Student's t-test. Categorical variables will be compared using the chi-square test or Fisher's exact test when appropriate.

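### The protocol body sets intention to treat, but the synopsis and SAP item 20 set a modified version whose removals are loosely worded, and the SAP plans no all-randomised analysis

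*SAP*

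**What the plan says.** Three places name the analysis population, and they do not agree.

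- Protocol 7.0 (Statistical Analysis): "Analyses will be based on the intention to treat".
- Protocol synopsis (Statistical methodology): "Analyses will be based on the modified intention to treat". The modification is not defined.
- SAP Section 4, item 20 (Analysis population): "Modified intent to treat (removing the participants that did not meet the inclusion criteria".

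Two neighbouring SAP items, under the heading on adherence and protocol deviations, describe ineligible participants in other words. Item 19c: "The only protocol deviations that were encountered in this trial were enrollment of participants that did not meet the inclusion/exclusion criteria". Item 19d, which is a sentence fragment: "Participants that did not meet inclusion/exclusion criteria and were withdrawn from the study by the treating physician or study staff".

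On design, Protocol 4.0 describes a "randomized, prospective, pragmatic open label pilot study" and adds: "Antiplatelet choice will ultimately be decided by the treating physician taking into account all clinical factors". Protocol 6.2 places the Arm 1 test after allocation: "If randomized to Arm 1 (genotyping arm), the research coordinator will obtain a buccal swab for the PGx test". SAP item 26a makes prasugrel or ticagrelor at discharge, within 7 days, the primary outcome.

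**The concern.** The SAP's rule takes randomised participants out of the analysis, which Protocol 7.0 does not provide for. The reader is also not told exactly who is taken out. Item 20 mentions only inclusion criteria, while items 19c and 19d mention both inclusion and exclusion criteria.

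The difference has consequences. Of the three inclusion criteria, only willingness to comply is open to judgement after entry. If exclusion criteria count as well, criterion 7 (the treating physician's objection to participation) comes into play.

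The person whose prescription is the primary outcome knows the arm, sees the genotype in Arm 1 and, under item 19d, may withdraw the participant. No rule limits removal to facts dated before randomisation. If removal were related to arm and to the drug chosen, the difference in proportions would no longer be a comparison of the randomised groups.

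**Working it through.** **1. Who is removed, by reading.**

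- Item 20 taken literally: those failing any of the 3 inclusion criteria.
- Item 19c: those failing any of the 3 inclusion or 7 exclusion criteria.
- Item 19d: the part of the 19c group that was also withdrawn by the physician or staff.

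Only item 20 defines an analysis set; 19c and 19d describe deviations. Item 20 may be shorthand for all eligibility criteria, but the text does not say so. The three readings can give different denominators.

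**2. Whether another item covers the gap.** SAP items 27a to 29 name no all-randomised or sensitivity population. Items 24a to 24c report withdrawal from follow-up, voluntary withdrawal and loss to follow-up, but not removals for ineligibility by arm. Item 28 covers only censoring for MACE.

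**3. The plan's own figure.** Protocol 7.5 and SAP item 11 use 35% against 20%, 80% power and alpha 0.05 (taken as two-sided). With pooled variance and mean proportion 0.275:

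n = [1.96·√(2·0.275·0.725) + 0.8416·√(0.35·0.65 + 0.20·0.80)]² / 0.15² = (1.2377 + 0.5239)² / 0.0225 = 137.9, so 138 per group. This matches and is not in dispute.

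**4. Size if some participants are removed.** The documents give no removal count. The values k = 5 and k = 10 are assumptions, per arm or from the one arm named. The start is 250 per arm with 88/250 against 50/250 users (35% of 250 is 87.5, rounded to 88), a difference of 15.2 points. With m = 250 − k:

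- Non-users from both arms: (88 − 50)/m = 38/245 = 15.5; 38/240 = 15.8.
- Non-users from Arm 1 only: 88/m − 0.20 = 15.9; 16.7.
- Users from Arm 1 only: (88 − k)/m − 0.20 = 83/245 − 0.20 = 13.9; 78/240 − 0.20 = 12.5.

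The false-positive rate (true 20% in both arms) and power (35% against 20%) come from exact binomial enumeration with the uncorrected chi-square test, two-sided 0.05.

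| Removed | False-positive rate, k = 5 / 10 | Difference (points), k = 5 / 10 |
|---|---|---|
| None | 5.0% | 15.2 |
| Non-users, both arms | 5.1% / 5.2% | 15.5 / 15.8 |
| Non-users, Arm 1 only | 5.2% / 5.6% | 15.9 / 16.7 |
| Users, Arm 1 only | 8.0% / 17.1% | 13.9 / 12.5 |

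In the last row the false positives run mostly against genotyping: 7.14 of 8.02 percentage points at k = 5, and 16.87 of 17.13 at k = 10.

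Power is 96.7% with no removal. Its lowest value in any pattern examined is 80.9%, when 10 users are removed from Arm 1 and 10 non-users from Arm 2.

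**5. Which pattern has support in the text.** Exclusions 2 and 3 (prior intracranial haemorrhage, TIA or stroke; active bleeding) overlap the cautions on prasugrel and ticagrelor in Protocol Table 1. That makes removal of non-users from both arms plausible, but only if exclusion criteria count under item 20. Its effect is negligible.

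**The case against.** The best defence is that item 20 settles the population for the SAP, and that its wording is loose rather than contradictory. Item 19c speaks of enrolling people who did not meet criteria, which points to ineligibility at entry. Exclusion 7 is an entry criterion, and nothing describes its use after randomisation. This largely stands. A reader might infer three rival definitions of the removed set, but the documents support only one definition with unclear scope.

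A reader might also infer that the trial never planned an all-randomised analysis. That goes too far: Protocol 7.0 plans intention to treat, and it is the SAP that does not carry it forward.

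Third, a reader might take the 17.1% as the chance of a false claim for genotyping. The documents do not support that. With 10 users removed from Arm 1, only 0.26 percentage points favour genotyping. To favour it falsely at that rate, users would have to be removed from the control arm, where genotype is not determined until the study ends and no mechanism is described.

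What remains is the conflict between Protocol 7.0 and the other two places, and a withdrawal route in item 19d that cannot be ruled out in an open-label trial.

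**Conclusion.** The point holds as an inconsistency that should be corrected, together with an unquantified risk of bias. It does not show that bias occurred. A reader might infer from item 19d that physicians withdrew participants because of arm or genotype; nothing in the documents says so.

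The direction of any effect is unknown. Under the assumed one-arm removals of 5 or 10 from Arm 1, the planned 15.2 points would move to between 12.5 and 16.7. The planned contrast would usually still be detected. What is exposed is the size of the estimate, and the error rate if the true difference is small. These figures rest on assumed counts, 250 per arm, and removal of users only or of non-users only.

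**What to change.** - Reconcile the synopsis, Protocol 7.0 and SAP item 20 to one population.
- Make the primary analysis of discharge drug all randomised participants by assigned arm, as Protocol 7.0 states, where the data exist and consent allows. The outcome falls within 7 days, so it should be available for most.
- Keep the modified set as a sensitivity analysis, limited to ineligibility documented from facts dated before randomisation.
- Use one eligibility wording in items 19c, 19d and 20, and say whether withdrawal is also required.
- Tabulate removals by arm, reason and timing. If they were few, balanced and based on entry facts, this table would largely settle the matter.
- For MACE and bleeding, also report an all-randomised analysis using follow-up available up to withdrawal. Item 28 already censors MACE at last known follow-up.

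The cost is wording changes and one rerun, because SAP item 14 reports the analyses as already performed. A few ineligible participants may slightly dilute the contrast. Later outcomes of withdrawn participants may not exist, which is why the clinical analyses stop at withdrawal.
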